The 7-day cut off derives from the data in the literature with respect to the average times of onset of the lesions (4th day in the medical field, 5° in the surgical field and 3° in the intensive care unit) with standard deviations that allow to affirm that after 7 days in the acute patients the PD event is extremely rare (Palese 2017; Chiari 2017; Santamaria 2015). PD is defined as a damage to the skin and underlying tissues due to pressure, stretching or friction or a combination of these factors (NPUAP 2014). The incidence of PD is represented by the PD who develop during hospitalization and are not present when the patient is admitted. The injuries will be classified according to the classification defined by the guideline prepared by NPUAP 2014. (attachment).

Secondary Endpoints:

- Incidence of PD to the sacrum category ≥ II ° according to the NPUAP scale
- Skin irritation / damage due to adhesive dressing
- Day of onset of the PD
- Number of dressings used
- Number of patients who stop treatment due to discomfort caused by the dressing (withdrawal)

Other study variables / data collected

- Gender
- Age

- Origin of the patient: first aid, another ward or facility, Short Observation (OBI), Home
- Pregressed (healed) PD to the sacred
- Patient risk level measured with the Braden scale (Pancorbo-Hidalgo PL 2006)
- Days in the study
- Use of the diaper
- Use of the bladder catheter
- Use of anti-decubitus surface (static, preventive dynamics, curative dynamics and air release)
- Daily presence of the caregiver (presence at least during a meal, never, always)

Study Population

Inclusion Criteria:

- Patients at risk of developing PD measured with the Braden scale (Braden \leq 16) with intact sacral skin and / or with signs of healing from previous sacral lesions.
- Patients or legal guardians who consent to the study
- Adult patients
- . Male and female gender
- Expected hospital stay and / or life expectancy > 72 hours
- Patients hospitalized for no more than 24 hours

Exclusion criteria:

- Patients with known allergy to the products under study or with dermatological pathologies that prevent the use of topical products
- Patient with, upon entering the ward, advanced preventive dressing in the sacral region

Design

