Trial randomizzato e controllato di superiorità in cieco (elaborazione dati) a gruppi paralleli con rapporto di allocazione di 1:1 con randomizzazione a blocchi di 10 e bilanciati per reparto e per area. Non è possibile la cecità degli outcome assesor in quanto nei pazienti del gruppo sperimentale resta spesso una traccia cutanea della presenza della schiuma (impronta cutanea).

Randomized controlled superiority trial (blinded only data processing) with parallel groups.

Allocation ratio of 1: 1 with randomization in blocks of 10 and balanced by department and

by area. The blindness of outcomes assesor is not possible as in the patients of the

experimental group there is often a cutaneous trace of the presence of the foam (skin

impression).

Materials and methods

Areas involved

Surgical Area: general or specialist surgery departments.

Medical Area: geriatrics or neurology or internal medicine departments.

Intensive Area: intensive care or intensive care units.

For each area of each participating center a sample of 40 subjects is expected, randomization

will be done by areas.

Intervention:

Application of MSP in the sacral region within 24 hours of admission and replaced when it

comes off, gets wet or gets dirty in addition to standard preventive care (see below).

MSP is a multilayer foam consisting of: a multi-layered dressing consisting of a polyurethane

foam and a super-absorbent hydrocapillary pad, two layers of polyurethane film, one external

and one internal, and a pressure-sensitive adhesive (PSA) that holds together the two

absorbent layers. The last layer, in contact with the lesion and the skin, is in delicate adhesive

silicone, non-adherent, perforated.

The foam must be raised to the margins at least once a day to check the condition of the

underlying skin. If on the seventh day after randomization the patient is still hospitalized,

after the inspection of the skin, the data collection form (CRF) is closed and the study

concluded.

The medication will be provided free of charge for all the subjects in the studio by the

manufacturer. The company will only supply the dressings. A written agreement was signed

in which the company agrees to provide free samples of the product being studied without

5 di 18

affecting in any way the methodology of drafting the protocol, conducting the study, analyzing the data and publishing the results.

Comparison:

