Standard preventive care. If on the seventh day after randomization the patient is still hospitalized, after the inspection of the skin, the CRF is closed and the study concluded.

Standard preventive care

Evaluation of the risk of developingPD with a Braden scale within 24 hours of admission. Positioning of the patient on a preventive or curative anti-decubitus mattress (static or alternating pressure) if Braden value ≤ 16 or in any case according to the hospital policy, daily inspection of the skin and mobilization of the patient at least every 4 hours (in the surgical patient at least in the post-operative period) if the clinical conditions allow it (NPUAP 2014). Management of incontinence, humidity control and prevention of skin maceration and rubbing / friction during postural changes as per hospital policy.

Method

At the entrance of the patient in the ward, the nurse dedicated to the first reception assesses whether the person has the necessary criteria to be enrolled in the study. In the positive case, he/she will explain to the patient or to his legal guardian, the rationale of the study, he/she will submit the information requesting consent to the participation granting the necessary time for reading and consultation before any consent and signature. If the patient consents, the nurse has the consent signed and attached to the medical record by setting the first part of the CRF (attachment). If the patient at risk refuses the participation, if he/she has other exclusion criteria or if it is not possible to collect the consent, the nurse transcribes it on the CRF and files it. If the patient agrees to participate in the study, the dedicated nurse proceeds to randomization (see below for methods) taking the first opaque envelope according to the external progressive number. It transcribes in the CRF the date, the patient's ID, if he already has PD not to the sacrum and their category and location. It also sign the study arm and other variables of interest. If the patient is in the experimental arm, the nurse, in addition to the standard preventive care, applies the MSP to the sacrum and writes date and time on the CRF and on the MPS. However, the foam must be applied within 24 hours of admission. If this

time interval is exceeded, the researcher will mark the problem in CRF in the "NOTES" part and the patient leaves the study and the CRF is archived.

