- Operating room: when the patient is eventually taken to the operating room to undergo surgery, the operating room nurse checks if the patient at risk is enrolled in the study. At the end of the surgical intervention, when returning to the ward, if the patient belongs to the MSP arm, check if the foam has been removed (surgery often necessary to proceed with the preparation of the sterile field for spinal anesthesia and for the procedure surgery) and repositions it.
- If the patient is transferred to the intensive care unit at any time during his or her treatment, the dedicated nurse will also enclose the data collection form with the documentation, which will continue to be filled in according to the protocol written by the dedicated intensive care nurse.
- If the patient leaves the operating room directly for intensive care, it is the duty of the dedicated nurse in the ward to send the CRF to the intensive care unit to continue the study, if it is not already attached (see previous paragraph). The Intensive care nurse will collect data with the same methods and timing.
- If the patient is transferred to a ward not involved in the study, the CRF is completed and the enrollment is closed (as if he were discharged).

Daily data collection

Every morning the data collection nurse:

- Assess the patient's skin (shoulder, sacrum, elbows, heels, back, calves, thighs, ankles...) and completed the daily CRF part;
- If the patient belongs to the intervention arm (MSP), the nurse will also check daily whether the dressing is still tight, dry and clean. If the dressing is detached even partially the MSP is replaced (do not put reinforcement patches) and the change is reported in the CRF.
- Every day (once a day) in patients with MSP, it removes an edge to check if the skin of the sacrum is still intact, marking the result of the inspection in the CRF.

- If it replaces the MSP (dirty, detached or wet) it marks it in the CRF and writes the date and time on the MPS itself. The foam will however be removed upon discharge regardless of the day of admission and in any case no more than 7 days (as per the indication of maximum permanence of the MSP provided by the manufacturer).
- Upon return of the patient from the operating room, the referring nurse verifies, as soon as possible, that the patient of the intervention arm still has the polyurethane foam in the sacrum. Otherwise apply it by marking it in the CRF.

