- At discharge or on the appearance of pressure lesion on the sacrum ≥ 2nd category, the CRF is closed and the patient ends the study. If the patient has developed PD the treatment of the lesion will be performed according to the hospital policy.
- The medication will be removed, however, no later than the first 7 days of admission after which the patient ends the study.

Study exit criteria

- Withdrawal of informed consent before randomization
- Not randomized within 24 hours of admission

Conclusion of the study in the single recruited subject

- Withdrawal of consent after randomization
- The appearance of irritation to the skin caused by the dressing. The dressing is removed, reported in CRF and irritation treated as per hospital policy.
- At the request of the patient due to discomfort due to preventive medication.
- On discharge / death / transfer to ward not involved in the study before the 7th day after randomization
- After 7 days from randomization in the absence of PD to the sacrum
- The appearance of pressure injury to the sacrum higher than the first category

Sample size

From a randomized monocentric study of at-risk patients with a hip fracture where polyurethane foams were used in prevention, the incidence in the experimental group was 4.5% while in the control group of 15.4%. Similar deltas had also been identified in other trials in intensive care patients. Assuming similar results in the population subject of the present study and taking into account an alpha error of 0.05 and a beta error of 20%, it is necessary to enroll at least 228 patients at risk. In order to allow analyzes by subgroup (see the "statistical analysis" section) the sample size must be guaranteed for each area (medical, surgical, intensive).

Taking into account also a possible loss at the follow-up of 10% and also assuming a 10% withdrawal rate, the necessary sample will be 280 patients per area and therefore a total of 840 patients (420 per arm). Each hospital involved will enroll 40 patients per area involved in that specific hospital.

Randomization

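### Three post-randomisation exit rules stop outcome collection almost only in the dressing arm, and nothing says how the missing 7-day outcome is counted under intention to treat

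*Combined protocol and SAP*

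**What the plan says.** The primary endpoint is a sacral lesion of any category detected in the first 7 days (Primary Endpoint). Statistical analysis states intention to treat and a Fisher exact test on incidences, without defining the population or mentioning missing outcomes.

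Three rules act after allocation:

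- **Late foam (Method).** The envelope is opened, the arm is recorded, and foam is applied if the patient is in the dressing arm. If the 24-hour limit has passed, "the patient leaves the study and the CRF is archived". A separate item under Study exit criteria, "Not randomized within 24 hours of admission", applies to both arms before allocation.
- **Irritation (Conclusion of the study in the single recruited subject).** "The appearance of irritation to the skin caused by the dressing" is listed as ending the study for that subject, as well as leading to removal of the dressing.
- **Discomfort (same list).** "At the request of the patient due to discomfort due to preventive medication". Secondary Endpoints agrees that this is an exit, since it counts the "Number of patients who stop treatment due to discomfort caused by the dressing (withdrawal").

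Other departures stay under observation. Under Possible deviations, a missing foam is replaced and noted, and a control patient found with foam is kept and handled as experimental. Under Daily data collection, the nurse checks the sacrum of dressing patients every day, "marking the result of the inspection in the CRF", so findings before an exit are on file.

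Design describes a "Randomized controlled superiority trial (blinded only data processing) with parallel groups" and accepts that outcome assessors cannot be blinded.

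**The concern.** Intention to treat needs an outcome, or a stated rule for a missing one, for every randomised patient. Here the plan stops looking at certain patients because of the dressing they were allocated. A control patient without foam cannot have it applied late, react to it or object to it. So 7-day outcomes can be lost unequally between arms for reasons tied to treatment.

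The loss may also be related to the outcome. Category I lesions count as primary events, and the Safety section admits that category I is hard to tell from skin redness. An unblinded nurse could therefore record redness under foam as dressing irritation, which ends follow-up, whereas a control patient without foam cannot receive that label. This is an inference, not something the documents state. Mean onset is given as day 3 to 5, so an early exit can come before many lesions.

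The effect on the result depends on the unstated counting rule:

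- **Exiters excluded:** the comparison favours the dressing if exiters are at higher risk, is neutral at equal risk, and goes slightly against the dressing at lower risk.
- **Exiters counted ulcer-free:** the dressing arm's observed incidence falls by whatever ulcers were not seen before exit.

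Blinded data processing limits choosing the rule by its result, but exit reasons that name the dressing could reveal the arm.

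**Working it through.** **The plan's own figures.** Sample size uses 15.4% v 4.5%, alpha 0.05 and power 80%. With a two-sided test (assumed; sidedness is not stated) and unpooled variance:

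2 × (1.960 + 0.842)² × (0.154 × 0.846 + 0.045 × 0.955) / (0.109)² = 228.9 in total, against the stated 228.

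Inflation for 10% loss and 10% withdrawal: 228 / (0.9 × 0.9) = 281.5, against the stated 280 per area; 3 × 280 = 840, or 420 per arm. The inflation suggests that such patients were expected to have no usable outcome, but the plan does not say so. It protects numbers, not comparability.

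**Assumed inputs.** The documents give no exit share by arm or cause and no risk for exiters; the 10% withdrawal is not arm-specific. So I vary:

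- f, the share of the dressing arm that exits: 2%, 5%, 10% (none in control);
- k, exiters' risk relative to the other dressing patients: 0.5, 1, 2;
- u, the share of exiters' ulcers not seen before exit: 0.5 or 1.

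**Formulas.** With overall risk p in the dressing arm, non-exiters have p_rest = p / (1 − f + fk). The control risk is 0.154.

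- Excluded: RR = p_rest / 0.154.
- Counted ulcer-free: RR = [(1 − f) p_rest + f k p_rest (1 − u)] / 0.154.

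**No true effect (p = 0.154 in both arms).** Worked examples:

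- f = 0.10, k = 2, excluded: 1/1.1 = 0.91.
- f = 0.10, k = 0.5, excluded: 1/0.95 = 1.05.
- f = 0.05, k = 1, u = 0.5: 0.95 + 0.025 = 0.975.
- f = 0.10, k = 2, u = 0.5: (0.9 + 0.1)/1.1 = 0.91.
- f = 0.10, k = 2, u = 1: 0.9/1.1 = 0.82.

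False-positive rates come from exact enumeration of two independent binomials with the two-sided Fisher test at p < 0.05, split by direction. Arm sizes are 420 v 420 for ulcer-free counting, and 399 or 378 v 420 for exclusion at 5% or 10% exits. With no exits the rate is 2.0% in each direction.

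RR, with the chance of a significant result wrongly favouring the dressing:

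| Counting rule | Exits | Equal risk (k = 1) | Twice the risk (k = 2) |
|---|---|---|---|
| Excluded | 5% | 1.00; 2.2% | 0.95; 4.3% |
| Excluded | 10% | 1.00; 2.2% | 0.91; 7.3% |
| Ulcer-free, half unseen | 2% | 0.99; 2.3% | 0.98; 2.7% |
| Ulcer-free, half unseen | 5% | 0.98; 2.9% | 0.95; 3.9% |
| Ulcer-free, half unseen | 10% | 0.95; 4.1% | 0.91; 6.9% |
| Ulcer-free, all unseen | 2% | 0.98; 2.7% | 0.96; 3.5% |
| Ulcer-free, all unseen | 5% | 0.95; 4.1% | 0.90; 7.3% |
| Ulcer-free, all unseen | 10% | 0.90; 7.7% | 0.82; 18.8% |

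At half the risk, exclusion gives RR 1.03 (5% exits) and 1.05 (10% exits). At 10% exits, 1.0% of trials favour the dressing and 4.5% favour control. The all-unseen rows are an upper bound, unlikely for most exiters because inspections before exit are recorded.

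**Planned effect (p = 0.045 in the dressing arm; 0.045/0.154 = 0.29).** At 10% exits, from twice to half the risk:

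- excluded: 0.27 to 0.31;
- half unseen: 0.27 to 0.29;
- all unseen: 0.24 to 0.28.

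**The case against.** - **Late foam is the weakest of the three rules.** Randomisation must already fall within 24 hours of admission, and application is the next step by the same nurse. The rule bites only if the window closes between envelope and foam. This stands: such exits are probably uncommon, and the weight rests on irritation and discomfort.
- **There may be an implicit counting rule.** The endpoint is what is detected in 7 days, so with intention to treat an undetected ulcer arguably counts as no event. That reading is possible but not stated. It is the ulcer-free scenario above, and it leaves the asymmetry in place.
- **The exclusion figures drop ulcers recorded before exit.** A category I lesion is already a primary event, keeps the patient in the study and is on the CRF, and a careful analysis would keep it. This is a fair caution on those rows. They show an ordinary complete-case analysis, which nothing in the plan rules out.
- **The larger figures stack assumptions.** All exits are in one arm, at double risk, with little seen beforehand. At equal risk with half unseen, 2% and 5% exits give only 2.3% and 2.9% against 2.0%. This stands too.
- **Discharge, death and transfer also cut follow-up short.** True, but those rules apply to both arms.

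**Conclusion.** The concern holds. Followed as written, the plan ends outcome collection for dressing-related reasons almost only in the dressing arm, assessors are unblinded, and no rule covers the missing outcome despite the stated intention to treat. The arm-specific loss is the main defect; the absent counting rule adds to it.

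The size is uncertain and probably modest. With no true effect, the chance of wrongly favouring the dressing rises from 2.0% to between 2.3% and 6.9% when exiters are counted ulcer-free with half their ulcers unseen, over 2% to 10% exits at equal or double risk. The upper bound is 18.8%. The bias can also run slightly against the dressing if lower-risk exiters are excluded. Under the planned effect the RR stays within 0.24 to 0.31. The problem therefore matters mainly if the true effect is small or absent. These figures rest on assumed exit shares and risks. The change should be made, with medium confidence in how much it matters.

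**What to change.** Reconcile Method, the two exit lists, Statistical analysis and Possible deviations so that stopping or not receiving the dressing is separate from ending follow-up.

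1. Record late application, irritation and discomfort as a deviation, treatment discontinuation or adverse event. Continue the existing daily sacral inspection and CRF to end points common to both arms: day 7, discharge, death, transfer to a non-participating ward, a sacral lesion of category II or higher, or withdrawal of consent to data collection. The CRF should distinguish a request to stop the dressing from withdrawal of consent.
2. Analyse every randomised patient in the allocated arm. State how a missing 7-day outcome is counted in the primary analysis, add a sensitivity analysis that varies the missing outcomes by arm, and report exits by reason and arm.

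Whether and when the dressing is applied or removed is left unchanged.

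The cost is protocol wording, minor CRF work, one extra analysis and the Ethics Committee amendment that the protocol requires for such changes. No new procedure is needed: daily skin inspection is standard care in both arms, and irritation and discomfort stops are already secondary endpoints. The observed effect may become less favourable to the dressing. Outcomes not collected after exit cannot be recovered by later analysis.

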The rationale for the use in prevention of products useful for the treatment of pressure injuries is also described in the 2013 systematic review (Moore 2013). The incidence of PD is probably reduced through the ability of foam dressings to redistribute mechanical forces. The Guidelines of the European and United States National Pressure Ulcer Advisory Panels (EPUAP and NPUAP) also suggest that the use of foam dressings may protect parts of the body at risk of stretch injuries. The market offers different types of advanced dressings compared to the material they are made of (hydrocolloids, polyurethane foams), their thickness (single or multi-layer) and their dimensions.

Various in vitro comparative studies are available where the different abilities of the main brands of dressings are compared with the pressure redistribution (Call 2015; Matsuzaki 2015; Miller 2015), liquid management (Young 2007) and shear forces (Levy 20015 and Levy 20016) which are the main causative factors of PD development (NPUAP 2014). In these in vitro studies the material that seems to be most effective is polyurethane foam (Matsuzaki 2015; Miller 2015), especially multilayer (Black 2015).

Two systematic reviews published in 2013 and 2014 then evaluated the efficacy on patients of using advanced multi-layer polyurethane dressings in prevention to reduce the incidence of pressure injuries (Clark 2014; Moore 2013). The results of both systematic reviews, although in favor of the use of dressings, are considered by the authors to be inconclusive due to the weakness of the study design found and therefore the high risk of bias. Both reviews concluded by soliciting the production of methodologically more rigorous clinical studies (Clark 2014; Moore 2013). Recently, some trials have been published which confirm the preventive efficacy of polyurethane multilayer foams (Santamaria 2015; Kalowes 2016; Forni 2018; Santamaria 2018) but the populations investigated are very specific, limiting the generalizability of results.

AIM

The aim of the present study was to assess whether the application of a multilayered dressing made of hydrocellular polyurethane foam conformed to the sacral area (MSP) in addition to standard preventive care reduces the rate of pressure ulcer (PU) and their severity in population at risck admitted in acute care Hospital.

Study endpoint

Primary Endpoint

Incidence of PD to the sacrum of any category detected during the first 7 days of hospitalization.

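### No recorded look at the uncovered sacrum is tied to dressing removal, so lesions under the foam can go unrecorded in the dressing arm only, which probably favours the dressing

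*Combined protocol and SAP*

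**What the plan says.** **Endpoint (Study endpoint, Primary Endpoint).** "Incidence of PD to the sacrum of any category detected during the first 7 days of hospitalization". Category I counts, and the event is defined by detection.

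**Daily check, dressing arm.** The Intervention section says "The foam must be raised to the margins at least once a day", to look at the skin beneath. Daily data collection says that once a day the nurse lifts the dressing: "it removes an edge to check if the skin of the sacrum is still intact". The two descriptions differ, and neither says how much of the covered area must be seen.

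**Daily check, control arm.** Standard preventive care asks for "daily inspection of the skin and mobilization of the patient at least every 4 hours", and Daily data collection has the sacrum assessed each morning. No study dressing is in the way.

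**Closure on day 7.** For patients still in hospital on the seventh day after randomization, the CRF closes after a skin inspection. In the Intervention section: "after the inspection of the skin, the data collection form (CRF) is closed". The Comparison section has the same rule. Neither says whether the foam is off at that point.

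**Removal.** Daily data collection says "The foam will however be removed upon discharge regardless of the day of admission", and at the latest at 7 days. It later puts removal within the first 7 days of admission, after which the patient ends the study. No inspection or CRF entry is attached to removal.

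**Earlier closure.** At discharge (Daily data collection) and on transfer to a non-participating ward (Method), the CRF is closed with no final inspection stated.

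**Blinding (Design).** Outcome assessors are not blinded, because the foam often leaves a mark on the skin.

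**The concern.** The endpoint should be ascertained in the same way in both arms. Here the dressing that is being tested also covers the area being assessed. A lesion near a lifted edge is visible; one under the centre may not be, and faint category I redness is the most exposed. This loss can arise only where there is foam, so it lowers the dressing-arm count.

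Removal is the one planned moment at which the whole sacrum comes into view in a dressing patient, and as written that view need not enter the data. The gap is clearest for patients who are discharged or transferred before day 7. The secondary endpoints of category II or higher and day of onset depend on the same view. Analysis can bound the effect of unseen lesions afterwards but cannot recover them.

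**Working it through.** **1. The plan's own figure.** Inputs from Sample size: 15.4% control, 4.5% dressing, alpha 0.05 (two-sided assumed), power 80%, allocation 1:1. With the unpooled normal formula:

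n per arm = (1.960 + 0.842)² × (0.154×0.846 + 0.045×0.955) / (0.154 − 0.045)² = 7.849 × 0.17326 / 0.011881 = 114.5

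That is 229 to 230 in total, within 2 of the stated 228. For losses of 10% and 10%, 228/0.81 = 281.5, close to the stated 280 per area; 3 × 280 = 840, or 420 per arm. The sample-size arithmetic is not at issue.

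**2. Which closures have a look at the uncovered sacrum?**

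| Exit | Removal ordered | Inspection before closure | Inspection stated to follow removal |
|---|---|---|---|
| Day 7 | Yes, by day 7 of admission | Yes | No |
| Discharge before day 7 | Yes | Not stated | No |
| Transfer to a non-study ward | Not stated separately; treated as discharge | Not stated | No |

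The clocks matter for the first row. Removal runs from admission and closure from randomization. Randomization must fall within 24 hours of admission, so day 7 of admission comes no later than day 7 after randomization. Patients who stay the full period are therefore probably uncovered at or near the last check, but the text does not say so.

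**3. Effect of a given loss.** Let m be the share of dressing-arm patients with a lesion whose lesion is never recorded, and let m = 0 in controls. The observed dressing-arm incidence is p × (1 − m), so the relative risk is multiplied by (1 − m). The documents give no value for m; 0 to 30% is an assumption. With no true effect, 420 per arm and the planned Fisher test at two-sided 0.05, exact enumeration gives the chance of a significant result in favour of the dressing:

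| m | Apparent RR | True incidence 10% (assumed) | True incidence 15.4% (plan's control figure) |
|---|---|---|---|
| 0 | 1.0 | 1.9% | 2.0% |
| 10% | 0.9 | 5.7% | 7.7% |
| 20% | 0.8 | 14.3% | 22.2% |
| 30% | 0.7 | 30.1% | 47.3% |

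The first row counts only the tail that favours the dressing; with both tails the rate at 15.4% is 4.0%.

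**4. Against the expected effect.** The plan's figures imply RR = 4.5/15.4 = 0.29. If 4.5% were observed with m = 20%, the true incidence would be 4.5/0.8 = 5.6% (RR 0.37); with m = 30%, 4.5/0.7 = 6.4% (RR 0.42). To create the whole contrast with no effect, m would have to be 1 − 4.5/15.4 = 71%.

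**5. The opposite error.** Suppose a skin impression is scored as category I. At 10% true incidence, m = 20% loses 2.0 events per 100 patients. False positives in 2.0/90 = 2.2% of the lesion-free dressing patients would cancel that loss. At 15.4% the figure is 3.08/84.6 = 3.6%.

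**The case against.** The strongest case on the other side has five parts.

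- **Full-stay patients are largely covered.** The foam is to be off by day 7 of admission, and a skin inspection is required on day 7 after randomization. A reader might infer that the CRF routinely closes without anyone seeing the uncovered sacrum; the documents do not support that. What stands is that the link is not written for these patients, and that no closing inspection is stated for those who leave earlier.
- **The stated purpose of the lift is to see the sacral skin.** How far the foam is peeled back is not specified, and a generous lift would miss little. That full exposure occurs in controls is likewise inferred. This limits the size of the problem; it does not supply the missing requirement.
- **There are other views.** Foam that is wet, dirty or detached is replaced, and it is often removed for surgery. These views occur in some patients only, with no full-sacrum record required. The CRF is an attachment that is not shown and may contain a suitable field.
- **The direction is not certain.** The Design section says the foam often marks the skin, and the Safety section concedes that category I is hard to tell from redness. An unblinded nurse could score the imprint as a lesion, and step 5 shows that a small rate would offset a 20% loss. This stands: the direction is probable only.
- **Repeated looks reduce misses.** The endpoint rationale puts mean onset at days 3 to 5, so a persisting lesion gets several checks. If three looks were independent, missing 30% of lesions overall would need about 67% missed per look (0.3^(1/3) = 0.67). Misses under the centre may well be correlated, so this does not rule out a material loss, but it is a reason not to take 30% as an expectation.

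**Conclusion.** The point holds as a gap in outcome ascertainment. The plan does not require the last recorded inspection in the dressing arm to be made with the dressing off, and it states no closing inspection for discharge or transfer before day 7. Lesions under the foam can therefore go unrecorded in that arm only, which probably favours the dressing.

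The size is unknown. The 8%, 22% and 47% figures, against 2% with equal detection, rest on assumed losses of 10%, 20% and 30%, no true effect, 15.4% incidence, complete detection in controls and no imprint misreadings. They illustrate a scenario and do not estimate this trial's bias. Nor do they support a reading in which missed lesions explain the whole expected benefit, since that would need 71% missed. The reasonable concern is an inflated effect. The point should be addressed; confidence is medium, because the depth of the daily lift and the content of the CRF are not known.

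**What to change.** In Intervention, Comparison and Daily data collection (including its closure rules), state that:

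1. At every CRF closure (day 7, discharge, transfer, or other exit where possible) the fully exposed sacrum is inspected and recorded in both arms; in the dressing arm this follows the removal already planned.
2. The same full view is recorded whenever a dressing is already being replaced.
3. Any lesion seen then counts as an event on that date.
4. A skin impression is recorded separately from a category I lesion.

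Reconcile the two descriptions of the daily lift, and the admission and randomization clocks. A sensitivity analysis over a range of missed fractions would show how far the result depends on detection.

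The cost is a few sentences and a small addition to the CRF, with no extra visit or dressing; the added work is a brief inspection and entry at closure. The downside is some additional dressing-arm events, a few of which may be imprints misread as category I just after removal. The category II or higher secondary endpoint, which should be less exposed to both errors, is a partial check. Lesions that resolve before closure will still be missed.
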